### 9.2. Treatment Compliance

Subjects are expected to take 1 drop of study medication per eye, once per day.

Treatment compliance for Stage 1, as a percentage, will be calculated as  $\text{compliance (\%)} = (\text{number of ampules used as determined in Interactive Response Technology}) / ((\text{Date of Last Dose of Stage 1} - \text{Date of First Dose of Stage 1}) + 1) \times 100$ . The number of actual doses withheld will be recorded in the eCRF.

Starting on the day of the Month 36 visit, subjects were switch to an electronic dosing diary. Each eye's dosing is collected independently, based on whether eye drops were applied or not for each eye. Any missing dosing information between Month 36 visit and last reported dose will be considered as missed dose(s). Treatment compliance for Stage 2, as a percentage, will be calculated as  $\text{compliance (\%)} = (\text{sum of number of reported doses} / ((\text{Date of Last Dose of Stage 2} - \text{Date of First Dose of Stage 2}) + 1)) \times 100$ .

Subjects will be considered compliant overall for study medication if the compliance is ≥80%. Descriptive statistics (number of subjects, mean, SD, minimum, median, and maximum) for number of ampules used (Stage 1), number of doses received (Stage 2) and treatment compliance will be summarized by treatment group for Safety Set by actual treatment and stage and for the ITT Set, the mITT Set, the PPS, and the mPPS by randomized treatment for each stage.

Given the duration a subject is enrolled in the study, it is possible for the subject to begin self-dosing instead of parental dosing. All subjects will be asked if this occurred and when the change occurred. The number and percentage of subject switching to self-dosing during the course of the study will be summarized by Stage 1 treatment group and overall.

### 9.3. Adverse Events

The analysis of AEs will be based on the concept of treatment-emergent AEs (TEAEs). An adverse event is any untoward medical occurrence associated with the use of a drug in humans, whether or not considered drug-related.

Treatment-emergent adverse events (TEAEs) of Stage 1 are defined as any new or worsening of existing adverse events that occur or worsen between start (or increase in intensity on or after the first dose date

This document is confidential.

of Stage 1 treatment on day 1) and the last dose date of Stage 1. TEAEs of Stage 2 are defined as any AE that occurs or worsens between the first dose date of Stage 2 and the last dose date of Stage 2.

The first dose date for Stage 1 is defined as the first dose of study medication received after randomization in Stage 1. The first dose date for Stage 2 is defined as the first dose of study medication received after the Stage 1 last dose date and subject is re-randomized. All adverse events (AEs) will be coded using the MedDRA version 20.1 or higher. The following listings of AEs will be provided by Stage and subjects:

- All AEs,
- Serious adverse events (SAEs) Serious ocular and non-ocular AEs, respectively
- All deaths
- TEAEs (overall, ocular, non-ocular, respectively) leading to study withdrawal
- TEAEs (overall, ocular, non-ocular, respectively) leading to study drug discontinuation
- Severe AEs
- Study drug related AEs
- Study drug related SAEs

Treatment-emergent adverse events will be included in summary tables by treatment received for each stage. Ocular TEAEs will be summarized separately from all other TEAEs. An overall summary table of TEAEs for each stage will be produced for the following categories:

- Any Ocular TEAE
- Severe Ocular TEAEs
- Study drug-related Ocular TEAEs
- Serious Ocular TEAEs
- Study drug-related Serious Ocular TEAEs
- Ocular TEAEs leading to study discontinuation
- Ocular TEAEs leading to death
- Any Non-Ocular TEAE
- Severe Non-Ocular TEAEs
- Study drug-related Non-Ocular TEAEs
- Serious Non-Ocular TEAEs
- Study drug-related Serious Non-Ocular TEAEs
- Non-Ocular TEAEs leading to study discontinuation
- Non-Ocular TEAEs leading to death

All TEAEs will be classified by System Organ Class (SOC) and Preferred Term (PT). Frequency count of TEAEs, the number of unique subjects experiencing a TEAE, percentage of unique subjects experiencing a TEAE, and total number of events will be tabulated by treatment and Stage for ocular and other TEAEs separately. For the number of unique subjects reporting, if a subject reported more than one TEAE that was coded to the same SOC or PT, the subject will be counted only once for that specific SOC or PT.

The following summaries of TEAEs will also be provided:

- TEAEs by SOC and PT
- Ocular TEAEs by SOC and PT
- Non-Ocular TEAEs by SOC and PT

This document is confidential.

- TEAEs by SOC, PT, and maximum severity
- Ocular TEAEs by SOC, PT, and maximum severity
- Non-Ocular TEAEs by SOC, PT, and maximum severity
- TEAEs by SOC, PT, and maximum relationship
- Ocular TEAEs by SOC, PT, and maximum relationship
- Non-Ocular TEAEs by SOC, PT, and maximum relationship
- Treatment-related TEAEs by SOC and PT
- Ocular Treatment-related TEAEs by SOC and PT
- Non-Ocular Treatment-related TEAEs by SOC and PT
- Serious TEAEs by SOC and PT
- Serious Ocular TEAEs by SOC and PT
- Serious Non-Ocular TEAEs by SOC and PT
- Serious treatment-related TEAEs by SOC and PT
- Serious Ocular treatment-related TEAEs by SOC and PT
- Serious Non-Ocular treatment-related TEAEs by SOC and PT
- TEAEs leading to study withdrawal by SOC and PT
- Ocular TEAEs leading to study withdrawal by SOC and PT
- Non-Ocular TEAEs leading to study withdrawal by SOC and PT
- TEAEs leading to study drug discontinuation by SOC and PT
- Ocular TEAEs leading to study drug discontinuation by SOC and PT
- Non-Ocular TEAEs leading to study drug discontinuation by SOC and PT
- TEAEs leading to death by SOC and PT
- Ocular TEAEs leading to death by SOC and PT
- Non-Ocular TEAEs leading to death by SOC and PT
- TEAEs associated with antimuscarinic function
- Ocular TEAEs associated with antimuscarinic function
- Non-Ocular TEAEs associated with antimuscarinic function
- TEAEs by SOC, PT and Sex
- Ocular TEAEs by SOC, PT and Sex
- Non-Ocular TEAEs by SOC, PT and Sex
- TEAEs by SOC, PT and Race
- Ocular TEAEs by SOC, PT and Race
- Non-Ocular TEAEs by SOC, PT and Race
- TEAEs by SOC, PT and Age
- Ocular TEAEs by SOC, PT and Age
- Non-Ocular TEAEs by SOC, PT and Age

For TEAEs presented by relationship to study treatment, the strongest relationship to study treatment(s) during the clinical trial will be presented for each subject if coded to the same SOC or PT. For TEAEs presented by severity, the worst severity during the clinical trial will be presented for each subject if coded to the same SOC or PT. If either relationship or severity is missing, then the strongest relationship (related) or worst severity (life-threatening) will be assigned. Adverse Events associated with antimuscarinic function are defined in Table 3.

This document is confidential.

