### 6.2. Key Definitions

Treatment-emergent adverse events (TEAEs) of Stage 1 are defined as any new or worsening of existing adverse events that occur or worsen between the first dose date of Stage 1 and the last dose date of Stage 1.

TEAEs of Stage 2 are defined as any AE the occurs or worsens between the first dose date of Stage 2 and the last dose date of Stage 2.

First dose date for Stage 1 is defined as the first dose of study medication received after randomization in Stage 1.

First dose date for Stage 2 is defined as the first dose of study medication received after the Stage 1 last dose date and subject is re-randomized.

For subjects who did not receive study medication in a given stage, leave first dose date for that stage as missing. If the first dose date is missing and if the subject is randomized, impute the missing first dose date using the randomization date in the analysis of Time to Change from Baseline in Myopia Progression of -0.75D (see 8.3.7 and 8.3.8).

Baseline for Stage 1 is defined as the last measurement prior to first dose of study medication in Stage 1, If an adverse event starts or non-study medication taken on the day of first dose it will be treated as occurring after treatment started. All other planned measurements are presumed to occur prior to first dose of study medication.

Baseline for Stage 2 will be defined as latest results prior to start of study medication in Stage 2, which occurs the day after the Month 36 visit. The results of the Month 36 visit will act as the baseline for Stage 2.

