## 9. Safety

The population used for safety analyses will be the Safety Set (SS). Safety will be assessed on the basis of ophthalmic safety assessments (BCVA, photopic pupil size, slit-lamp examination (SLE), dilated fundus examination, and tonometry), HR, and adverse events (AE). Safety Tables will be provided separately for each stage of the study.

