## 11. Interim Analyses

In order to determine the efficacy of Atropine Sulfate Ophthalmic Solution in progression of childhood myopia, an analysis will be performed after all subjects complete or withdraw from Stage 1. At that time, on Stage 1 treatment assignments will be unblinded and no analyses or summaries will be provided for Stage 2 results. All study personnel, not including Investigators, site staff, and clinical research associates (CRAs), may be unblinded for Stage 1 at this time.

All analyses will be performed as documented in the SAP. No decisions regarding the study or changes in the study are to be made at that time.

This document is confidential.

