	14.3.1.2.1.3	Non-Ocular Treatment-Emergent Adverse Events by System Organ Class and Preferred Term - Stage 1	Stage 1 Safety Set
	14.3.1.2.2.1	Treatment-Emergent Adverse Events by System Organ Class and Preferred Term - Stage 2	Stage 2 Safety Set
	14.3.1.2.2.2	Ocular Treatment-Emergent Adverse Events by System Organ Class and Preferred Term - Stage 2	Stage 2 Safety Set

This document is confidential.

Header	Table Number	Name	Analysis Set
	14.3.1.2.2.3	Non-Ocular Treatment-Emergent Adverse Events by System Organ Class and Preferred Term - Stage 2	Stage 2 Safety Set
	14.3.1.3.1.1	Treatment-Emergent Adverse Events by System Organ Class, Preferred Term, and Maximum Severity – Stage 1	Stage 1 Safety Set
	14.3.1.3.1.2	Ocular Treatment-Emergent Adverse Events by System Organ Class, Preferred Term, and Maximum Severity – Stage 1	Stage 1 Safety Set
	14.3.1.3.1.3	Non-Ocular Treatment-Emergent Adverse Events by System Organ Class, Preferred Term, and Maximum Severity – Stage 1	Stage 1 Safety Set
	14.3.1.3.2.1	Treatment-Emergent Adverse Events by System Organ Class, Preferred Term, and Maximum Severity – Stage 2	Stage 2 Safety Set
	14.3.1.3.2.2	Ocular Treatment-Emergent Adverse Events by System Organ Class, Preferred Term, and Maximum Severity – Stage 2	Stage 2 Safety Set
	14.3.1.3.2.3	Non-Ocular Treatment-Emergent Adverse Events by System Organ Class, Preferred Term, and Maximum Severity – Stage 2	Stage 2 Safety Set
	14.3.1.4.1.1	Treatment-Emergent Adverse Events by System Organ Class, Preferred Term, and Relationship to Study Drug – Stage 1	Stage 1 Safety Set
	14.3.1.4.1.2	Ocular Treatment-Emergent Adverse Events by System Organ Class, Preferred Term, and Relationship to Study Drug – Stage 1	Stage 1 Safety Set
	14.3.1.4.1.3	Non-Ocular Treatment-Emergent Adverse Events by System Organ Class, Preferred Term, and Relationship to Study Drug – Stage 1	Stage 1 Safety Set
	14.3.1.4.2.1	Treatment-Emergent Adverse Events by System Organ Class, Preferred Term, and Relationship to Study Drug – Stage 2	Stage 2 Safety Set
	14.3.1.4.2.2	Ocular Treatment-Emergent Adverse Events by System Organ Class, Preferred Term, and Relationship to Study Drug – Stage 2	Stage 2 Safety Set
	14.3.1.4.2.3	Non-Ocular Treatment-Emergent Adverse Events by System Organ Class, Preferred Term, and Relationship to Study Drug – Stage 2	Stage 2 Safety Set
	14.3.1.5.1.1	Treatment-Related Treatment-Emergent Adverse Events by System Organ Class and Preferred Term – Stage 1	Stage 1 Safety Set

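### SAP 9.3 takes the worst severity and strongest relationship over the whole trial, but the tables are by stage and children are re-randomized between stages, so a category from one stage can be shown under the other stage's treatment

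*SAP*

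**What the plan says.** SAP 9.3 has one rule for the severity shown for a child: "the worst severity during the clinical trial will be presented for each subject if coded to the same SOC or PT". A parallel sentence covers causality: "the strongest relationship to study treatment(s) during the clinical trial will be presented for each subject". Neither sentence names a stage.

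The tables that use the rule are organized by stage. SAP 9 says "Safety Tables will be provided separately for each stage of the study", and SAP 9.3 says "Treatment-emergent adverse events will be included in summary tables by treatment received for each stage". The Index of Tables (SAP 16) lists, for example, "Treatment-Emergent Adverse Events by System Organ Class, Preferred Term, and Maximum Severity – Stage 1", with a Stage 2 counterpart and a matching pair for relationship.

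Each stage also has its own event window. A Stage 1 TEAE must "occur or worsen between the first dose date of Stage 1 and the last dose date of Stage 1" (SAP 6.2). For Stage 2 the window runs "between the first dose date of Stage 2 and the last dose date of Stage 2".

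Between the stages the treatment changes for most children. Under SAP 3.6.2, children from either atropine arm are re-randomized 1:1:1 to Vehicle, 0.01% or 0.02%. Children from the Vehicle arm are re-randomized 1:1 to 0.01% or 0.02%, with no Vehicle option.

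**The concern.** A table by maximum severity or by relationship is read as a statement about the treatment at the head of the column. If the maximum runs over the whole trial, the category in a column may come from an event on a different treatment, a year or more away. Safety is part of the primary objective, and these tables show how bad the events were and how far the investigators attributed them to the drug.

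The re-randomization makes this more than a technicality. Nobody on Vehicle in Stage 1 can be allocated Vehicle again, and nobody can be allocated Vehicle in Stage 2 without having been allocated atropine in Stage 1. Under a trial-wide maximum, neither Vehicle column is protected from atropine-period categories.

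**Working it through.** **1. Tables affected.** There are two displays (maximum severity, relationship), two stages and three event groupings (all, ocular, non-ocular): 2 × 2 × 3 = 12 tables. In SAP 16 these are 14.3.1.3.1.1 to .3, 14.3.1.3.2.1 to .3, 14.3.1.4.1.1 to .3 and 14.3.1.4.2.1 to .3.

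**2. The rules side by side.**
- Which events qualify for a table: the stage-specific TEAE windows in SAP 6.2 and 9.3.
- Which treatment heads the column: the treatment received in that stage (SAP 5.2 and 9.3).
- Which category is shown for a child who is counted: the two sentences in SAP 9.3, whose window is the clinical trial.

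The first two rules are tied to a stage and the third is not. The third is the only rule that says which category is displayed.

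**3. What a carry-over needs.** The child must have a TEAE in each stage in the same SOC or PT, and the category in the other stage must be the worse one. In the SOC row the two events need not share a preferred term. As a hypothetical case, take a child on 0.02% in Stage 1 with a severe, related event, who is re-randomized to Vehicle and has a mild, unrelated event of the same term in Stage 2. Read literally, the Stage 2 Vehicle column shows that child as severe and related. The child is in that column either way, so only the category changes.

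**4. How many children could be exposed.** Inputs: planned numbers of 138 Vehicle, 138 on 0.01% and 207 on 0.02%; Stage 1 drop-out of 27%, about 10% per year (protocol synopsis).
- The plan's own figures reproduce: 1 − 0.9³ = 27.1%, and 207 × 0.73 = 151.1, in line with its statement of at least 150 children on 0.02%.
- Continuing from Vehicle: 138 × 0.73 = 100.7. Continuing from 0.01%: also 100.7.
- Assume that all who remain are re-randomized. The Stage 2 Vehicle column then holds (100.7 + 151.1) / 3 = about 84 children, all allocated atropine in Stage 1.
- About 101 Stage 1 Vehicle children continue, all allocated atropine in Stage 2.
- Children whose allocation changes: 100.7 + (2/3) × 251.9 = 268.6 of 352.6, or 76%.

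These counts say who could be affected. They do not estimate how many categories would change, which depends on adverse event rates by term and stage. The documents give none.

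**The case against.** The strongest reply is that the sentence is already limited by context. It concerns TEAEs presented by severity, the tables present one stage at a time, and a Stage 2 event falls outside the Stage 1 window. SAP 5.2 adds that displays with data from both stages use the treatment sequence, so a Stage 2 category under a Stage 1 label would go against the SAP's own labelling rule. This stands as evidence of intent: a within-stage maximum is very probably what was meant. It does not settle the text. Those provisions decide which events enter a table and how a cross-stage table is labelled. None of them overrides the sentence that selects the category, and a programmer would have to depart from that sentence to get the intended table.

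Three stronger readings are tempting, and the documents do not support them.
- A reader might infer that Stage 2 results leak into the Stage 1 analysis. On the planned dates (first subject November 2017, Stage 1 complete August 2022) Stage 2 events would exist by then. But SAP 11 says that at that time "no analyses or summaries will be provided for Stage 2 results", which bars this use.
- A reader might infer that the Stage 1 contrast between Vehicle and atropine shrinks. All continuing Vehicle children are allocated atropine in Stage 2, but so are two thirds of those from each atropine arm. A longer window can only raise categories, and it can do so in every arm. The net direction is not established.
- A reader might want a percentage of categories affected. Any such figure would rest entirely on assumed recurrence and worsening rates.

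**Conclusion.** The point holds as a conflict between two sentences of SAP 9.3 and the by-stage design of the tables they govern. It does not show that the tables will be built wrongly. The Stage 2 tables are the clearest case, because Stage 1 data are complete when they are run and the restriction in SAP 11 applies only to the Stage 1 analysis. Stage 1 tables are exposed only if they are re-run after Stage 2, which the documents do not say will happen.

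The consequence is limited to the severity or relationship category of children already counted under that SOC or PT. Incidence counts, alpha, power and sample size are untouched. The exposed columns (about 84 Stage 2 Vehicle children, and about 101 continuing Stage 1 Vehicle children if those tables are re-run) rest on the planned numbers, 27% drop-out and full re-randomization of those who remain. This is a minor point, worth correcting because the correction is so small.

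**What to change.** In both sentences of SAP 9.3, for relationship and for severity, replace *during the clinical trial* with *among TEAEs of the stage being tabulated*. That brings the selection rule into line with the TEAE windows in SAP 6.2 and 9.3, the by-stage tables in SAP 9 and 16, and the bar on Stage 2 summaries in SAP 11. The cost is a few words in the SAP and a check that the table programs take the maximum within stage. No new data, tables or analyses are needed.

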**Table 3: Adverse Events Associated with Antimuscarinic Function**

Classification	Preferred Term
Ophthalmic	Photophobia
	Dyschromatopsia
	Night blindness
	Angle closure glaucoma
	Lacrimation decreased
Non-Ophthalmic	Blood pressure increased
	Heart rate increased
	Dry skin
	Dry mouth
	Dry throat
	Restlessness
	Irritability
	Delirium
	Flushing
	Seizure
	Epilepsy
	Urinary retention
	Obstruction gastric
	Bronchial secretion retention
	Arrhythmia

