#### **Data and Safety Monitoring Plan:**

To minimize risk and ensure the immediate safety of study subjects, both local and systemic anticholinergic and other potential effects of study medication will be measured at each visit. Parameters such as heart rate, mydriasis, photophobia, blurred near vision, ocular and conjunctival inflammation and allergic reactions to study medication will be carefully and routinely monitored to assess both safety and tolerability.

All safety data will be collected and entered in the eCRF allowing for real-time review. Medical review will be performed concurrently with Data Management's review of data and issue of queries to sites. The aim of the medical review is to monitor eligibility issues, assess potential protocol deviations and identify safety issues.

In addition, the peer-reviewed and grey literature as well as global databases of AEs from other atropine products will be routinely and continually monitored.

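### SAP Table 3 defines the antimuscarinic adverse events without mydriasis or any near-blur or accommodation term, so events coded that way fall outside the tables built on it

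*SAP*

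**What the plan says.** The protocol synopsis, under its Data and Safety Monitoring Plan, commits to broad surveillance: "both local and systemic anticholinergic and other potential effects of study medication will be measured at each visit". It then gives examples: "Parameters such as heart rate, mydriasis, photophobia, blurred near vision, ocular and conjunctival inflammation", followed by allergic reactions.

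SAP Section 9.3 plans a targeted set of adverse event summaries. Among them is "Ocular TEAEs associated with antimuscarinic function", alongside an overall and a non-ocular counterpart. The index of tables (SAP Section 16) numbers these 14.3.1.11.x for each stage, laid out by system organ class (SOC) and preferred term (PT). Membership is fixed by one sentence: "Adverse Events associated with antimuscarinic function are defined in Table 3". That table is titled "Adverse Events Associated with Antimuscarinic Function". Nothing marks the list as a set of examples.

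The ophthalmic block of Table 3 has five preferred terms: night blindness, dyschromatopsia, photophobia, angle closure glaucoma and "Lacrimation decreased". The non-ophthalmic block has 15, including "Heart rate increased".

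**The concern.** Mydriasis and blurred near vision are two of the ocular effects that the protocol itself picks out for attention, and neither has a term in the list that defines the antimuscarinic subset. A reader who turns to the 14.3.1.11 tables to see how often atropine-type effects occurred on 0.02%, 0.01% and vehicle would find no row for either, however many were reported. The tables would look complete, and nothing in their titles would say otherwise.

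At stake is the content of one group of descriptive safety tables. No efficacy analysis, alpha allocation or data collection is affected.

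**Working it through.** The plan states no figure to reproduce. The check compares terms, with one illustration of scale.

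**Step 1. Compare the lists.** Left: the first four effects named in the protocol's monitoring plan. Right: SAP Table 3, searched for mydriasis, pupil, blur, vision, accommodation, photophobia and heart rate.

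| Effect named in the protocol | Term in Table 3 |
|---|---|
| Heart rate | Heart rate increased |
| Mydriasis | none (also nothing on the pupil) |
| Photophobia | Photophobia |
| Blurred near vision | none (nothing on blur, vision or accommodation) |

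Two of these four are covered; of the three ocular ones, only photophobia. The protocol's list goes on to inflammation and allergic reactions, which one would not expect in an antimuscarinic grouping and which are not counted here.

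**Step 2. Is the list closed?** Section 9.3 makes Table 3 the definition, and its 5 + 15 = 20 terms read as complete, with no sign of redaction. Followed as written, the programming excludes any event coded to an unlisted term from every 14.3.1.11 table.

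**Step 3. Does separate measurement explain the omission?** Pupil size is summarised under SAP 9.6 and near acuity under SAP 9.5. Heart rate is likewise summarised under SAP 9.4, yet has its own Table 3 term. Having a separate measurement summary is therefore not the rule by which terms were left off.

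**Step 4. Can other outputs fill the gap?** In part. The ocular table by SOC and PT shows each term by arm. Section 9.3 counts a subject once per SOC or PT, so PT rows cannot be added to give the number of children with any of several events. The measurement summaries are descriptive statistics at six-month visits, whereas adverse events are also collected at the three-month visits and telephone checks.

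**Step 5. Scale, by assumption only.** Let p be the share of subjects who have a mydriasis or near-blur event and no Table 3 event. The documents give no p. With n planned subjects (SAP 3.6.1: 207 on 0.02%; 138 in each other arm), the expected number missing is n × p, and the chance of at least one is 1 − (1 − p)^n.

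| Assumed p | 207 × p | 138 × p | 1 − (1 − p)^207 |
|---|---|---|---|
| 0.5% | 1.0 | 0.7 | 65% |
| 1% | 2.1 | 1.4 | 88% |
| 2% | 4.1 | 2.8 | 98.5% |
| 5% | 10.4 | 6.9 | >99.9% |

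The same p in both columns shows scale only; it says nothing about how p differs between arms.

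**The case against.** The strongest reply is that the two documents do not contradict each other. The protocol text is a monitoring plan, its list is illustrative, and it covers other effects besides anticholinergic ones. It does not promise that each monitored parameter becomes a term in a particular adverse event table. That stands: the omission is a gap in the SAP's grouping, not a breach of a protocol commitment.

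Second, the information is reported elsewhere. That also stands as to data: any mydriasis or blur event appears with subject counts by arm in the general ocular tables, and the underlying measurements have their own summaries. It does not justify the list, because heart rate is treated both ways.

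Third, the ophthalmic list was revised deliberately: the SAP revision history records an update in version 1.1. It gives no reason for leaving out effects that the protocol names, so the revision shows that the list was considered but does not explain it.

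Fourth, the wording matters. The protocol says blurred near vision. A general blurred-vision term is wider and, in this population, may reflect progressing myopia. This stands and shapes the fix.

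Finally, a reader might infer that the tables will undercount atropine effects and so understate the difference between active and vehicle. The documents do not support that. They give no event rates; the shortfall is zero if no such event is reported; and a narrower difference would require these events to be more frequent on active drug, which cannot be derived here. The SAP also plans no test on these tables and does not expressly call for a pooled any-event row, so the loss of a combined incidence cannot be asserted.

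**Conclusion.** The point holds as a defect of classification and presentation. Table 3 is the definition; it has no mydriasis, near-blur or accommodation term; and the protocol names mydriasis and blurred near vision for monitoring. Events coded to those terms are excluded from the 14.3.1.11 tables, which can understate antimuscarinic events there.

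The omission can be read directly from the text. Its numerical effect cannot: the range of about 1 to 10 children on 0.02% rests wholly on the assumed 0.5% to 5%, and neither the size nor the direction of any between-arm effect follows from the documents. It is worth correcting because the change is small and alters what the tables report.

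**What to change.** Add to the ophthalmic block of Table 3 the preferred term for mydriasis and those for near blur and accommodation, taking exact names from the MedDRA version used for coding. If the general blurred-vision term is also included, show it as its own row with a note that it may reflect myopia progression. If the sponsor prefers to keep the list as it is, the SAP should give the reason and cross-refer to the pupil size and near acuity outputs.

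If Stage 1 is already unblinded, present the expanded grouping as a labelled additional Stage 1 table beside the planned one, and prespecify it for Stage 2.

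The cost is a few rows in one SAP table and reruns of the 14.3.1.11 outputs; no new data are needed. The downside is that the reported antimuscarinic incidence may rise and a few blur events of other origin may enter.
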